8.4 Adequacy of Protection Against Risks

8.4.1 Protections against Risk

To decrease the possibility of infection at the site of blood drawing, the area on the arm above the vein where blood will be taken will be prepped with 70% isopropyl alcohol antiseptic prior to venipuncture.

Subjects/subject's LAR(s) will be counseled on possible side effects following vaccination and followed closely in the immediate post-vaccination period and during the following week for assessment of moderate to severe local or systemic reactogenicity. In the immediate post-vaccination period, all subjects will be monitored in a sitting or lying position for 30 minutes following vaccinations to help prevent fainting, and injuries caused by a fall. Subjects with a prior history of severe allergic reaction after a previous dose of any influenza vaccine or COVID-19 vaccine, or to a vaccine component, including egg protein, will be excluded from study enrollment. Epinephrine and equipment for managing an airway will be available for immediate use if needed to treat a severe allergic reaction or anaphylaxis. Subjects will be evaluated and cared for as described in the Unscheduled Visit section above

Data Safety monitoring, as described above (**Section 5.4.3**), shall also be done.

The study team will provide documentation to the participant and primary care provider regarding receipt of COVID-19 vaccine and influenza vaccine. Documentation of COVID-19 vaccine receipt will be provided on the date received. Documentation of influenza vaccine receipt will be provided at Visit 2 when it can be assured that all participants will have received an influenza vaccine.

Participants will be counseled that if they are concerned that they have an influenza-like illness (characterized by fever and irritability, cough, sore throat, or vomiting) or symptoms of COVID-19 which may overlap with influenza, they should seek care for with their health care provider. If the provider suspects or determines that the participant has influenza, there are medications to treat influenza illness and the provider may opt to treat the participant with one of these medications. If a participant's care requires the identity of the date of receipt of influenza vaccine, blinding will be broken for that patient. At the end of the study, the participants/participant's LAR(s) and providers will receive documentation about the timing of influenza vaccination for each participant. If influenza activity become widespread, study enrollment may be paused. The National Institutes of Health (NIH) provides treatment and management recommendations for COVID-19 patients <https://www.covid19treatmentguidelines.nih.gov/>.

Every effort possible will be made to keep information about participants confidential. Computerized participant information will be kept in password-protected files on secured servers. Paper case report forms will be kept in locked files belonging to the study personnel. Any publications resulting from this work will not contain any identifiable participant information.

The CDC provides a Certificate of Confidentiality to protect the privacy of research participants. This certificate limits the disclosure of subject identifiable information. The investigators cannot disclose identifiable information except for if required by law, if participant consented to disclosure or if the information is used for other scientific research. Information may be disclosed to the CDC or the FDA.

8.4.2 ClinicalTrials.gov Requirements

The project is registered on ClinicalTrials.gov (NCT05028361).

8.5 Human Subjects

In obtaining and documenting informed consent, the Investigator and study team will comply with the applicable regulatory requirements, Good Clinical Practices, and ethical principles. The written informed consent form must be signed and dated by the study participant prior to initiation of any study activities.

APPENDIX

Appendix A: EQ-5D-5L and VAS

Appendix B: Corticosteroid Dose Charts

Appendix A: EQ-5D-5L and VAS

Cuestionario de Salud

Versión en español para los EE. UU.

(Spanish version for the USA)

Debajo de cada encabezamiento, marque UNA casilla, la que mejor describe su salud HOY.

MOVILIDAD

No tengo problemas para caminar

Tengo problemas leves para caminar

Tengo problemas moderados para caminar

Tengo problemas graves para caminar

No puedo caminar

CUIDADO PERSONAL

No tengo problemas para lavarme o vestirme solo/a

Tengo problemas leves para lavarme o vestirme solo/a

Tengo problemas moderados para lavarme o vestirme solo/a

Tengo problemas graves para lavarme o vestirme solo/a

No puedo lavarme o vestirme solo/a

ACTIVIDADES DE TODOS LOS DÍAS (Ej.: trabajar, estudiar, hacer las tareas domésticas, actividades familiares o actividades de ocio)

No tengo problemas para realizar mis actividades de todos los días

Tengo problemas leves para realizar mis actividades de todos los días

Tengo problemas moderados para realizar mis actividades de todos los días

Tengo problemas graves para realizar mis actividades de todos los días

No puedo realizar mis actividades de todos los días

DOLOR / MALESTAR

No tengo dolor ni malestar

Tengo dolor o malestar leve

Tengo dolor o malestar moderado

Tengo dolor o malestar intenso

Tengo dolor o malestar extremo

ANSIEDAD / DEPRESIÓN

[figure not shown]
No estoy ansioso/a ni deprimido/a

Estoy levemente ansioso/a o deprimido/a

Estoy moderadamente ansioso/a o deprimido/a

Estoy muy ansioso/a o deprimido/a

Estoy extremadamente ansioso/a o deprimido/a

Health Questionnaire

English version for the USA

Under each heading, please check the ONE box that best describes your health TODAY.

MOBILITY

I have no problems walking

I have slight problems walking

I have moderate problems walking

I have severe problems walking

I am unable to walk

SELF-CARE

I have no problems washing or dressing myself

I have slight problems washing or dressing myself

I have moderate problems washing or dressing myself

I have severe problems washing or dressing myself

I am unable to wash or dress myself

USUAL ACTIVITIES (e.g. work, study, housework, family or leisure activities)

I have no problems doing my usual activities

I have slight problems doing my usual activities

I have moderate problems doing my usual activities

I have severe problems doing my usual activities

I am unable to do my usual activities

PAIN / DISCOMFORT

I have no pain or discomfort

I have slight pain or discomfort

I have moderate pain or discomfort

I have severe pain or discomfort

I have extreme pain or discomfort

ANXIETY / DEPRESSION

[figure not shown]
I am not anxious or depressed

I am slightly anxious or depressed

I am moderately anxious or depressed

I am severely anxious or depressed

I am extremely anxious or depressed

Appendix B: Corticosteroid Dose Charts

0-4 years of age			5-11 years of age			>.12 years of age			
Daily Dose	Low	Medium*	High*	Low	Medium*	High*	Low	Medium*	High*
MEDICATION									
BeclomethasoneMDI*	N/A	N/A	N/A	80-160 mcg	>160-320 mcg	>320 mcg	80-240 mcg	>240-480 mcg	>480 mcg
40 mcg/puff				1-2 puffs 2x/day	3-4 puffs 2x/day		1-3 puffs 2x/day	4-6 puffs 2x/day	
80 mcg/puff				1 puff 2x/day	2 puffs 2x/day	.3 puffs 2x/day	1 puff am, 2 puffs pm	2-3 puffs 2x/day	.4 puffs 2x/day
Budesonide op1t	N/A	N/A	N/A	180-360 mcg	>360-720 mcg	>720 mcg	180-540 mcg	>540-1,080 mcg	>1,080 mcg
90 mcg/inhalation				1-2 inh's 2x/day	3-4 inh's 2x/day		1-3 inh's 2x/day		
180 mcg/inhalation					2 inh's 2x/day	.3 inh's 2x/day	1inh' am, 2 inh's pm	2-3 inh's 2x/day	.4 inh's 2x/day
Budesonide Nebules	0.25-0.5 mg	>0.5-1.0 mg	>1.0mg	0.5mg	1.0 mg	2.0mg	N/A	N/A	N/A
0.25 mg	1-2 nebs/day			1 neb' 2x/day					
0.5 mg	1neb'/day	2 nebs/day	3 nebs/day	1neb'/day	1neb' 2x/day				
1.0mg		1neb'/day	2 nebs/day		1neb'/day	1neb' 2x/day			
Ciclesonide MOit	N/A	N/A	N/A	80-160 mcg	>160-320 mcg	>320 mcg	160-320 mcg	>320--640 mcg	>640 mcg
80 mcg/puff				1-2puffs/day	1puff am, 2 puffs pm- 2 puffs 2x/day	.3 puffs 2x/day	1-2 puffs 2x/day	3-4 puffs 2x/day	
160 mcg/puff				1puff/day	1puff 2x/day	.2 puffs 2x/day		2 puffs 2x/day	.3 puffs 2x/day
Flunisolide MOit	N/A	N/A	N/A	160 mcg	320-480 mcg	.480 mcg	320 mcg	>320--640 mcg	>640 mcg
80 mcg/puff				1puff 2x/day	2-3 puffs 2x/day	.4 puffs 2x/day	2 puffs 2x/day	3-4 puffs 2x/day	.5 puffs 2x/day

Daily Dose	0-4 years of age			5-11 years of age			≥12 years of age		
	Low	Medium*	High*	Low	Medium*	High*	Low	Medium*	High*
MEDICATION									
Fluticasone MDI[†]	176 mcg	>176-352 mcg	>352 mcg	88-176 mcg	>176-352 mcg	>352 mcg	88-264 mcg	>264-440 mcg	>440 mcg
44 mcg/puff	2 puffs 2x/day	3-4 puffs 2x/day		1-2 puffs 2x/day	3-4 puffs 2x/day		1-3 puffs 2x/day		
110 mcg/puff		1 puff 2x/day	≥2 puffs 2x/day		1 puff 2x/day	≥2 puffs 2x/day		2 puffs 2x/day	3 puffs 2x/day
220 mcg/puff								1 puffs 2x/day	≥2 puffs 2x/day
Fluticasone DPI[†]	N/A	N/A	N/A	100-200 mcg	>200-400 mcg	>400 mcg	100-300 mcg	>300-500 mcg	>500 mcg
50 mcg/inhalation				1-2 inh [†] 2x/day	3-4 inh [†] 2x/day		1-3 inh [†] 2x/day		
100 mcg/inhalation				1 inh [†] 2x/day	2 inh [†] 2x/day	>2 inh [†] 2x/day		2 inh [†] 2x/day	≥3 inh [†] 2x/day
250 mcg/inhalation						1 inh [†] 2x/day		1 inh [†] 2x/day	≥2 inh [†] 2x/day
Mometasone DPI[†]	N/A	N/A	N/A	110 mcg	220-440 mcg	>440 mcg	110-220 mcg	>220-440 mcg	>440 mcg
110 mcg/inhalation				1 inh [†] /day	1-2 inh [†] 2x/day	≥3 inh [†] 2x/day	1-2 inh [†] pm	3-4 inh [†] pm or 2 inh [†] 2x/day	≥3 inh [†] 2x/day
220 mcg/inhalation					1-2 inh [†] /day	≥3 inh [†] divided in 2 doses	1 inh [†] pm	1 inh [†] 2x/day or 2 inh [†] pm	≥3 inh [†] divided in 2 doses

* It is preferable to use a higher mcg/puff or mcg/inhalation formulation to achieve as low a number of puffs or inhalations as possible.

[†] Abbreviations: DPI, dry powder inhaler (requires deep, fast inhalation); inh, inhalation; MDI, metered dose inhaler (releases a puff of medication); neb, nebulizer.

Adapted from NAEPP Expert Report 3 and https://www.nhlbi.nih.gov/files/docs/guidelines/asthma_qrg.pdf

## 1 INTRODUCTION

This document describes the statistical procedures that will be utilized for the CISA protocol Safety of Simultaneous versus Sequential Administration of mRNA COVID-19 Vaccines and Quadrivalent Inactivated Influenza (IIV4) in Adults, Adolescents and Children: A Randomized Observer Blinded Study that was approved on September 30, 2021. This statistical analysis plan (SAP) describes the methods of statistical analysis. The initial draft SAP (Version 0.1) was developed prior to any data being analyzed in order to avoid bias. Any subsequent changes that occur to the study protocol and requires changes to the analysis procedures will be documented in the SAP (both draft versions (0.X) and the final version (X.0)). Table 1 below will be used for tracking of changes to the SAP. In this study 450 persons age  $\geq$ 5 years are randomized 1:1 to receive either IIV4 or saline placebo injection by an unblinded vaccinator at Visit 1. Those receiving quadrivalent inactivated influenza vaccine (IIV4) at visit 1 will receive saline placebo at Visit 2 and those receiving saline placebo at Visit 1 will receive IIV4 at Visit 2. Randomization will be stratified by age (5 to < 12 years of age, 12 to < 18 years of age, 18 to <65 years of age, and  $\geq$  65 years of age) and receipt of either a primary two-dose series or booster dose of mRNA COVID-19 vaccine (for the  $\geq$ 18 age groups) using a permuted block randomization scheme stratified by Lead and Contributing Sites [Duke University (Lead); Johns Hopkins University (Contributing); Cincinnati Children's Hospital (Contributing)]. An interim data analysis will be conducted for data collected in the 2021-22 flu season. This interim data analysis will include blinded data from selected secondary and exploratory measures. This data will be presented to the study team and potentially the Safety Panel. More details will be provided in the Interim Data Analysis Plan.

Table 1. Statistical Analysis Plan Versions

Version	Date of Approval	Major Changes from Prior Version
0.1	TBD	NA
0.2	TBD	Addition of EO6: comparisons by vaccine product
0.3	TBD	Minor edits and modifications based on CDC review and discussion. Addition of Section 9 for a sensitivity analysis if a participant receives the incorrect study product of IIV4 and placebo.
0.4	TDB	Addition of EO8 SARS-CoV-2 serum antibody assessments. Minor edits to align with protocol amendment and comments CDC review.
1.0	3/2/2023	Minor edits provided by the CDC.

## 2 PROTOCOL OBJECTIVES

### 2.1 Primary

- a) PO1: To compare the proportion of participants with moderate or more severe fever, chills, myalgia, or arthralgia in the group receiving IIV4 simultaneously with mRNA COVID-19 vaccine at Vaccination Visit 1 (Simultaneous group) with the group receiving IIV4 alone one to two weeks later at Vaccination Visit 2 (Sequential group) following both Vaccination Visit 1 and 2

*Research hypothesis: The proportion of participants with moderate or more severe fever, chills, myalgia or arthralgia will be noninferior (not higher) in the Simultaneous group versus the Sequential group.*

## **2.2 Secondary**

- a) SO1: To compare the proportion of participants with moderate or more severe fever, chills, myalgia, or arthralgia in the Simultaneous versus the Sequential Group following the first vaccination visit.
- b) SO2: To compare the proportion of participants with moderate or more severe fever, chills, myalgia, or arthralgia in the Simultaneous versus Sequential Group following the second vaccination visit.
- c) SO3: To describe the proportions of participants in the Simultaneous and Sequential vaccination groups with solicited local and systemic reactogenicity events according to severity grade after the first and second vaccination visit and third vaccination visit for those receiving two doses of mRNA COVID-19 vaccine.
- d) SO4: To describe the proportions of participants in the Simultaneous and Sequential vaccination groups experiencing at least one serious adverse event and a description of these events.

## **2.3 Exploratory**

- a) EO1: To compare the proportion of participants with moderate or more severe fever, chills, myalgia, or arthralgia in the Simultaneous versus Sequential Group following the third vaccination visit for those receiving two doses of mRNA COVID-19 vaccine.
- b) EO2: To further characterize and describe the proportion of participants in the Simultaneous and Sequential groups with local or systemic reactogenicity events of greater severity following each vaccination visit and cumulatively.
- c) EO3: To describe the proportion of participants in Simultaneous and Sequential groups experiencing at least one unsolicited adverse event and one adverse event of special interest and to characterize these events.
- d) EO4: To compare the change of health-related quality of life (HRQOL) from baseline in the Simultaneous versus Sequential groups following the Vaccination Visit 1.
- e) EO5: To assess the safety profiles in the simultaneous and sequential group participants by baseline COVID-19 serostatus (positive versus negative). To be included, the blood needs to be collected within the protocol specified window and have a definitive result.
- f) EO6: To assess the safety profiles in the simultaneous and sequential group participants by COVID-19 vaccine product (Pfizer or Moderna).
- g) EO7: To assess the effect of simultaneous administration of IIV4 and COVID-19 vaccine on IIV4 immunogenicity as assessed by hemagglutination inhibition assay (HAI).
- h) EO8: To assess serum antibody levels to SARS-CoV-2 antigens.

### 3 STUDY ENDPOINTS

#### 3.1 Primary

- a) POM1a: Comparison of the proportion of participants reporting at least one solicited reactogenicity event to include fever, chills, myalgia, or arthralgia of moderate or greater severity in the Simultaneous group with the Sequential group within 1-7 days following Vaccination Visit 1 visit during which participants receive either IIV4 or placebo with an mRNA COVID-19 vaccine.

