2 STUDY OBJECTIVES AND OUTCOME MEASURES

OBJECTIVE	OUTCOME
Primary	
1. To compare the proportion of participants with moderate or more severe fever, chills, myalgia, or arthralgia in the group receiving IIV4 simultaneously with mRNA COVID-19 vaccine at Vaccination Visit 1 (Simultaneous group) with the group receiving IIV4 alone one to two weeks later at Vaccination Visit 2 (Sequential group) following both Vaccination Visit 1 and 2 Hypothesis: The proportion of participants with moderate or more severe fever, chills, myalgia or arthralgia will be noninferior (not higher) in the Simultaneous group versus the Sequential group.	1a. Comparison of the proportion of participants reporting at least one solicited reactogenicity event to include fever, chills, myalgia, or arthralgia of moderate or greater severity in the Simultaneous group with the Sequential group within 1-7 days following both Vaccination Visit 1 and Vaccination Visit 2
Secondary	
1. To compare the proportion of participants with moderate or more severe fever, chills, myalgia, or arthralgia in the Simultaneous versus the Sequential Group following the first vaccination visit	1a. Comparison of the proportion of participants reporting at least one solicited reactogenicity event to include fever, chills, myalgia, or arthralgia of moderate or greater severity in the Simultaneous group with the Sequential group within 1-7 days following Vaccination Visit 1 visit during which participants receive either IIV4 or placebo with an mRNA COVID-19 vaccine

2. To compare the proportion of participants with moderate or more severe fever, chills, myalgia, or arthralgia in the Simultaneous versus Sequential Group following the second vaccination visit	2a. Comparison of the proportion of participants reporting at least one solicited reactogenicity event to include fever, chills, myalgia, or arthralgia of moderate or greater severity in the Simultaneous group with the Sequential group within 1-7 days following Vaccination Visit 2 during which participants receive either IIV4 or placebo without an mRNA COVID-19 vaccine

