7.1.2 Analysis Populations

Full Analysis Population 1:

- This population is defined as all subjects who are randomized, vaccinated, and provide at least one day of complete data on the symptom diary.

Full Analysis Population 2:

- This population is defined as all subjects who are randomized and vaccinated.

Immunogenicity Population:

- This population defined as subjects who received vaccine, provide baseline and Visit 3 and Visit 4 blood draws of acceptable volume and quality within the protocol-defined time frame with no protocol violations affecting immunogenicity. Protocol violations affecting the immunogenicity analyses will be defined in the Statistical Analysis Plan (SAP). The acceptable visit window for sample analysis will be -7/+14 days from the target date. Any subject with sufficient data for either or both of the influenza and SARS-CoV-2 analysis will be included in this population. Should 10% or more of the total study population be excluded from the Immunogenicity Population due to missing the visit window, then an additional analysis will be performed including these subjects with the missing visit window exclusion.

The Full Analysis Population 1 is the primary population for analysis unless otherwise stated.

7.1.3 Primary Objective 1

- To compare the proportion of participants with moderate or more severe fever, chills, myalgia, or arthralgia in the group receiving IIV4 simultaneously with mRNA COVID-19 vaccine at Vaccination Visit 1 (Simultaneous group) with the group receiving IIV4 alone one to two weeks later at Vaccination Visit 2 (Sequential group) following both Vaccination Visit 1 and 2
 - Hypothesis: The proportion of participants with moderate or more severe fever, chills, myalgia or arthralgia will be noninferior (not higher) in the Simultaneous group versus the Sequential group.

This objective will be assessed for visits 1 and 2 using a one-sided noninferiority test with the alpha level set at 0.025 and noninferiority margin of 10%. The null hypothesis is the Simultaneous group is inferior (i.e., Simultaneous group will have a higher proportion) to the Sequential group in regards to the proportion of participants with at least one moderate or severe fever, chills, myalgia, or arthralgia event after visits 1 and 2.

Ho: Simultaneous group - Sequential group ≥ 0.10 (10%)

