#### 3.2 Secondary

- a) SOM1a: Comparison of the proportion of participants reporting at least one solicited reactogenicity event to include fever, chills, myalgia, or arthralgia of moderate or greater severity in the Simultaneous group with the Sequential group within 1-7 days following Vaccination Visit 1 visit during which participants receive either IIV4 or placebo with an mRNA COVID-19 vaccine.
- b) SOM2a: Comparison of the proportion of participants reporting at least one solicited reactogenicity event to include fever, chills, myalgia, or arthralgia of moderate or greater severity in the Simultaneous group with the Sequential group within 1-7 days following Vaccination Visit 2 during which participants receive either IIV4 or placebo without an mRNA COVID-19 vaccine.
- c) SOM3a: The proportion of participants in each vaccination group reporting specified solicited local and systemic reactogenicity events of any severity and by severity grade within 1-7 days following the first vaccination visit during which participants receive either IIV4 or placebo with an mRNA COVID-19 vaccine.

SOM3b: The proportion of participants in each vaccination group reporting specified solicited local and systemic reactogenicity events of any severity and by severity grade within 1-7 days following the second vaccination visit during which participants receive either IIV4 or placebo.

SOM3c: The proportion of participants in each vaccination group reporting specified solicited local and systemic reactogenicity events of any severity and by severity grade within 1-7 days following the third vaccination visit during which all participants receive an mRNA COVID-19 vaccine alone for those receiving two doses of mRNA COVID-19 vaccine.

- d) SOM4a: The proportion of participants in Simultaneous and Sequential Groups with at least one serious adverse event occurring during the study period and a description of each event.

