#### **5.2 Analytic Issues**

There are three study sites participating in the study and analysis of the primary objective will be stratified by site (Duke, Boston, Cincinnati) to account for this unit of randomization. All objectives will be stratified by site when applicable. There is one primary objective being evaluated, using a noninferiority hypothesis at the one-sided alpha 0.025 level. Otherwise, the alpha level will be set at two-sided alpha 0.05 for the secondary objectives and all exploratory objectives.

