## 8 ANALYSIS OF STUDY OBJECTIVES

### 8.1 Primary Objective

1. To compare the proportion of participants with moderate or more severe fever, chills, myalgia, or arthralgia in the group receiving IIV4 simultaneously with mRNA COVID-19 vaccine at Vaccination Visit 1 (Simultaneous group) with the group receiving IIV4 alone two weeks later at Vaccination Visit 2 (Sequential group) following both Vaccination Visit 1 and 2.
  - o *Research hypothesis: The proportion of participants with moderate or more severe fever, chills, myalgia or arthralgia will be noninferior (not higher) in the Simultaneous group versus the Sequential group.*

This objective will be assessed for visits 1 and 2 using a one-sided noninferiority test with the alpha level set at 0.025 and noninferiority margin of 10%. The null hypothesis is the Simultaneous group is inferior (i.e., Simultaneous group will have a higher proportion) to the Sequential group in regards to the proportion of participants with at least one moderate or severe fever, chills, myalgia, or arthralgia event after visits 1 and 2.

$$H_0: \text{Simultaneous group} - \text{Sequential group} \geq 0.10 \text{ (10\%)}$$

The alternative hypothesis is the Simultaneous group is noninferior to the Sequential group in regards to the proportion of participants with at least one moderate or severe fever, chills, myalgia, or arthralgia event after visits 1 and 2.

$$H_a: \text{Simultaneous group} - \text{Sequential group} < 0.10 \text{ (10\%)}$$

The upper bound of a site-stratified Newcombe binomial confidence interval (Yan and Su 2010) with Cochran-Mantel-Haenszel (CMH) weighting of the difference will be used to make these assessments with no adjustment to the alpha level for multiple comparisons.

See Tables 1 and 2 below for details.

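### SAP 3.1 defines the sole primary endpoint on Visit 1 only, duplicating secondary endpoint SOM1a and contradicting the protocol and the SAP's own primary objective and hypotheses, which use Visits 1 and 2

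*SAP*

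**What the plan says.** **SAP 3.1, POM1a.** The primary endpoint compares the groups on moderate-or-worse fever, chills, myalgia or arthralgia "within 1-7 days following Vaccination Visit 1 visit during which participants receive either IIV4 or placebo with an mRNA COVID-19 vaccine". Visit 2 is not mentioned.

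**SAP 3.2, SOM1a.** The first secondary endpoint begins "SOM1a: Comparison of the proportion of participants reporting at least one solicited reactogenicity event to include fever, chills, myalgia, or arthralgia" and continues with the same severity threshold, groups and Visit 1 window. Apart from the label, the two entries are identical.

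**Other statements of the primary question:**
- Protocol section 2, outcome 1a: "within 1-7 days following both Vaccination Visit 1 and Vaccination Visit 2". The Protocol Summary has the same window.
- Protocol 7.1.3: "This objective will be assessed for visits 1 and 2 using a one-sided noninferiority test".
- SAP 2.1, PO1, compares the Simultaneous group with the group given IIV4 "later at Vaccination Visit 2 (Sequential group) following both Vaccination Visit 1 and 2".
- SAP 8.1: "This objective will be assessed for visits 1 and 2 using a one-sided noninferiority test with the alpha level set at 0.025". Its null and alternative hypotheses concern the "proportion of participants with at least one moderate or severe fever, chills, myalgia, or arthralgia event after visits 1 and 2".

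**SAP 5.2** confines confirmatory testing to one question: "There is one primary objective being evaluated, using a noninferiority hypothesis at the one-sided alpha 0.025 level".

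The version table in SAP section 1 runs to the approved version 1.0 and lists no change of primary endpoint.

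**The concern.** Section 3 is where the SAP defines its endpoints, and for the only confirmatory endpoint it conflicts with the protocol and with SAP 2.1 and 8.1.

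The two windows address different questions. At Visit 1 the Simultaneous group receives COVID-19 vaccine plus IIV4, and the Sequential group receives COVID-19 vaccine plus saline. At Visit 2 the Sequential group receives IIV4 and the Simultaneous group receives saline. Visit 1 alone therefore compares two vaccines with one. Visits 1 and 2 together compare two schedules that deliver the same vaccines, which is the question posed by the title and the primary objective. The single-visit comparisons already have their own place as SO1 and SO2.

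If POM1a were followed, the primary outcome would duplicate SOM1a, the Sequential group's reactions to IIV4 would not count, and the schedule comparison would have no defined endpoint.

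**Working it through.** **1. Reproduce the plan's power (SAP 4.3).** Inputs: 15% in the Sequential group, margin 10 points, one-sided alpha 0.025, 214 per group. The Simultaneous rate is not stated; 15% is assumed (true difference 0).

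- Standard error = sqrt(2 × 0.15 × 0.85 / 214) = 0.03452.
- Power = Φ(0.10 / 0.03452 − 1.96) = Φ(0.937) = 82.56%, against 82.6% stated.
- Exact enumeration with the unstratified Newcombe upper limit: 82.2%.

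The sample-size arithmetic is not in dispute.

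**2. Can the two definitions disagree on one data set?** Newcombe upper limit: U = d + sqrt[(u_Sim − p_Sim)² + (p_Seq − l_Seq)²], where d is the difference (Simultaneous minus Sequential) and l and u are Wilson 95% limits. The counts are hypothetical, with 214 per arm.

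- Visit 1 only, 38 against 26 participants with events: 17.76% − 12.15% = 5.61 points. U = 5.61 + sqrt[(23.43 − 17.76)² + (12.15 − 8.43)²] = 12.4 points. Noninferiority is not shown.
- Suppose 2 more Simultaneous and 10 more Sequential participants have a first event after Visit 2, giving 40 against 36: 18.69% − 16.82% = 1.87 points. U = 1.87 + sqrt[(24.45 − 18.69)² + (16.82 − 12.41)²] = 9.1 points. Noninferiority is shown.

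**3. How often would the answers differ?** The documents give no visit-level rates for this endpoint, so the rates below are assumptions. Combined rate = 1 − (1 − p_V1)(1 − p_V2), which treats the visits as independent. P is the exact probability that U falls below 10 points, with 214 per arm and site stratification ignored.

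| Visit 1, Sim / Seq | Visit 2, saline (Sim) / IIV4 (Seq) | Visit 1 difference, points | Combined, Sim / Seq | P, Visit 1 only | P, combined |
|---|---|---|---|---|---|
| 15% / 15% | 2% / 2% | 0 | 16.7% / 16.7% | 82.2% | 79.2% |
| 13% / 12% | 2% / 3% | 1 | 14.7% / 14.6% | 79.5% | 82.1% |
| 15% / 13% | 2% / 3% | 2 | 16.7% / 15.6% | 65.9% | 70.6% |
| 16% / 12% | 1% / 5% | 4 | 16.8% / 16.4% | 42.8% | 75.6% |
| 17% / 12% | 2% / 5% | 5 | 18.7% / 16.4% | 31.1% | 56.0% |
| 20% / 15% | 2% / 5% | 5 | 21.6% / 19.25% | 27.8% | 50.3% |
| 19% / 12% | 1% / 5% | 7 | 19.8% / 16.4% | 13.7% | 42.8% |

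In the last four rows the combined Sequential rate is 16.4% to 19.25%, above the planned 15%.

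**4. The same check at the planned 15%.** Hold the combined rate at 15% in both groups, so combined power stays at 82.6% (normal approximation). Let f be the share of Sequential participants, and g the share of Simultaneous participants, whose first qualifying event comes only after Visit 2. The Visit 1 rates are then 15% − g (Simultaneous) and 15% − f (Sequential).

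For f = 3% and g = 1%: rates 14% and 12%, standard error sqrt[(0.14 × 0.86 + 0.12 × 0.88) / 214] = 0.0325, power Φ(0.08 / 0.0325 − 1.96) = 69.2%.

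Other values of Visit-1-only power:
- f = 1%, g = 0: 75.3%
- f = 5%, g = 1%: 48.1%
- f = 5%, g = 0: 34.8%
- f = g = 1%: 84.6%
- f = g = 2%: 86.8%

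When f = g, the two definitions perform about alike.

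**The case against.** The strongest reply is that POM1a is a copying slip. Every other statement of the primary question uses both visits, and SAP 8.1, which holds the test, margin and hypotheses, does so too. A careful programmer would probably follow 8.1. That is plausible, and it argues against reading POM1a as a deliberate change of endpoint. It does not remove the error, because no rule in the SAP gives 8.1 precedence over the endpoint section.

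A second reply concerns size. The large contrasts need a Simultaneous excess of 4 to 7 points at Visit 1 and a gap of 3 to 4 points between IIV4 and saline at Visit 2. Smaller gaps bring the two probabilities close together, and with no group difference at either visit the order reverses. This stands: the magnitude is a range that includes almost no effect. Some imbalance in first events after Visit 2 is still to be expected, since one group receives active vaccine and the other saline.

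A reader might also infer from SAP 8.1 that two unadjusted primary tests are planned, because it speaks of assessments in the plural and disclaims a multiplicity adjustment. Another might infer that an event is required after each visit. The documents support neither. SAP 5.2 names one primary objective, 8.1 has a single pair of hypotheses, and its wording of at least one event fits the union of the two windows. Stating the combining rule would help, but this is a secondary point of wording.

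**Conclusion.** The concern holds. POM1a is wrong as written: it duplicates SOM1a and contradicts protocol outcome 1a, protocol 7.1.3, PO1 and SAP 8.1. This follows from the text alone. It matters because the definition concerns the trial's only confirmatory endpoint.

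The consequence is conditional. A reader might infer that the primary hypothesis necessarily has two answers. The documents support only that it can: the results part to the extent that first qualifying events after Visit 2 are unequal between groups. The range in the working depends on assumed rates, independent visits (step 3) and no site stratification. Nor does the point imply that the trial is underpowered for its intended endpoint, since the stated power reproduces. Severity rests on the contradiction and not on any one illustrated gap in power.

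**What to change.** 1. In SAP 3.1, replace POM1a with protocol outcome 1a and state the combining rule: the participant has at least one grade 2 or higher fever, chills, myalgia or arthralgia on Days 1-7 after Visit 1 OR Days 1-7 after Visit 2, counted once per participant, with one noninferiority test.
2. Keep the visit-specific comparisons as SO1 and SO2, with SOM1a unchanged.
3. As a secondary edit, make the plural reference to assessments singular in SAP 8.1 and in the matching text of protocol 7.1.3.

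Replacing POM1a changes SAP wording only. The third edit, and stating the combining rule in the protocol as well, would also touch protocol text. No new data are needed, and the sample size is unaffected.
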